5.4.2.2 Time-to-Event

The following time-to-event analyses will be performed by dose level and overall for events occurred after date of first study drug dosing:

- a) Time to first CDA
- b) Time to first CR
- c) Time to first ECP
- d) Time to first relapse (after CDA has been achieved, as per the definition of relapse) after first dose of study drug
- e) Time to first increase in PDAI

For each event listed above, the number of days to the event will be calculated as:

(Date of first occurrence of event – Date of first study drug dosing of the dose level where the event is observed) + 1

The number of days to first occurrence of each event (a to d) will be summarized by descriptive statistics for each dose level and overall.

Patients who did not achieve the specific event are censored at the last day in a dose level or date of study completion/discontinuation.

Kaplan-Meier estimates of quartiles in days and their associated 80% and 95% CI will be calculated by using the LOGLOG transformation. Minimum and maximum survival times in days as well as number of the patients and the probability of experiencing the event on or before specific date will be provided in a table.

A sensitivity analysis using the Completer and PP populations will be provided.

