141 DAYS	xx.x (xx)	xx.x (xx)	xx.x (xx)	xx.x (xx)
169 DAYS	xx.x (xx)	xx.x (xx)	xx.x (xx)	xx.x (xx)

Note: Patients are classified into different dose levels according to the maximum dose they received during the 12 week treatment period. Control of disease activity (CDA) is defined as the time at which new lesions cease to form and established lesions begin to heal.

[1] Time to first CDA = Date of first CDA confirmed - Date of first dose + 1. Patients who did not achieve CDA by the date of study completion or discontinuation were censored at the date of completion or discontinuation respectively. 80% and 95% confidence intervals are calculated using the LOGLOG transformation.

[2] * indicate that this value is from a censored data.

[3] Kaplan-Meier estimate of the probability of experiencing the event on or before the specified timepoint (n' = number of patients remaining at risk beyond the specified timepoint).

Source Data: Listing 16.2.4.1.6

<DIRECTORY PATH>PROGRAM NAME Executed: DDMMYYYY hh:mm

Repeat the table above with the following population.

Table 14.2.3.1.2

Time to First Control of Disease Activity (CDA): Kaplan Meier Estimates
mITT Population

Table 14.2.3.1.3

Time to First Control of Disease Activity (CDA): Kaplan Meier Estimates
Per Protocol Population

Table 14.2.3.2.1
Time to First Complete Response (CR): Kaplan Meier Estimates
ITT Population

	400 mg (N=xx)	500 mg (N=xx)	600 mg (N=xx)	Total (N=xx)
TIME TO FIRST CR (days) [1]				
n	xx	xx	xx	xx
25% QUARTILE	xx.x	xx.x	xx.x	xx.x
80% CONFIDENCE INTERVAL	(xx.x, xx.x)	(xx.x, xx.x)	(xx.x, xx.x)	(xx.x, xx.x)
95% CONFIDENCE INTERVAL	(xx.x, xx.x)	(xx.x, xx.x)	(xx.x, xx.x)	(xx.x, xx.x)
MEDIAN	xx.x	xx.x	xx.x	xx.x
80% CONFIDENCE INTERVAL	(xx.x, xx.x)	(xx.x, xx.x)	(xx.x, xx.x)	(xx.x, xx.x)
95% CONFIDENCE INTERVAL	(xx.x, xx.x)	(xx.x, xx.x)	(xx.x, xx.x)	(xx.x, xx.x)
75% QUARTILE	xx.x	xx.x	xx.x	xx.x
80% CONFIDENCE INTERVAL	(xx.x, xx.x)	(xx.x, xx.x)	(xx.x, xx.x)	(xx.x, xx.x)
95% CONFIDENCE INTERVAL	(xx.x, xx.x)	(xx.x, xx.x)	(xx.x, xx.x)	(xx.x, xx.x)
MIN, MAX [2]	xx, xx	xx, xx*	xx, xx	xx*, xx
KAPLAN-MEIER ESTIMATE % (n') [3]				
15 DAYS	xx.x (xx)	xx.x (xx)	xx.x (xx)	xx.x (xx)
29 DAYS	xx.x (xx)	xx.x (xx)	xx.x (xx)	xx.x (xx)
57 DAYS	xx.x (xx)	xx.x (xx)	xx.x (xx)	xx.x (xx)
85 DAYS	xx.x (xx)	xx.x (xx)	xx.x (xx)	xx.x (xx)
113 DAYS	xx.x (xx)	xx.x (xx)	xx.x (xx)	xx.x (xx)
141 DAYS	xx.x (xx)	xx.x (xx)	xx.x (xx)	xx.x (xx)
169 DAYS	xx.x (xx)	xx.x (xx)	xx.x (xx)	xx.x (xx)

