2.2 Study Design

This is a Phase 2, open-label, pilot cohort study to evaluate the safety, clinical activity, pharmacodynamics, and pharmacodynamics of PRN1008 in patients with newly diagnosed or relapsing PV. An open-label design was chosen for several reasons: PV does not spontaneously remit so there is no placebo effect to account for; clinicians need to know when to use rescue CSs, if necessary, in a timely manner; and lastly, the pilot nature of the investigation itself is best explored in an open-label fashion.

Up to 28 days before enrollment in the study, patients will be required to sign an informed consent form, after which screening assessments will be carried out. Patients must fulfill all entry criteria to be enrolled into the study. Patients who fail to meet the entry criteria may be rescreened at the discretion of the Investigator. Up to 25 male or female patients with newly diagnosed (i.e., naïve to an effective induction treatment regimen) or relapsing, biopsy-proven, mild or moderate PV patients (Pemphigus Disease Activity Index [PDAI] 8 to 45) to enrolled into each parts of the study.

In Part A, the initial dosing was 400 mg twice daily (bid). The duration of study therapy was 12 weeks starting on Day 1 and ending on study Day 84 (total duration of individual subject participation is 28 weeks), with follow-up visits (off-treatment) until Week 29.

In Part B, the initial dosing is 400 mg once daily (qd), with intra-patient dose escalation to 400 mg bid allowed at or after the Week 3 visit for insufficient clinical response (and then again to 600 mg bid if necessary at or after the Week 5 visit). The duration of study therapy is 24 weeks starting on Day 1 and ending on study Day 169, with a follow-up visit (off-treatment) on Day 197 (Week 29). The total duration of individual subject participation is approximately 32 weeks.

Dose Escalation Rules Part B

Current Dose	Inadequate Clinical Response* Dose-Escalation Rules
400 mg qd	Increase to 400 mg bid (allowed at Week 3 visit or later)**
400 mg bid	Increase to 600 mg bid (allowed at Week 5 visit or later)**
600 mg bid	No dose increase possible.

* Investigator discretion: Generally, clinical response is shown by some improvement seen in first 2 weeks with CDA achieved by the Week 5 visit

** Unless tolerability issues preclude dose-escalation

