2.7 Schedule of Assessments

Table 1 Schedule of Assessments – Part B (24-weeks Treatment/ 4-weeks Follow Up)

	Screen	Day 1, Week 1 Pre-dose	Day 1 Week 1 Post-dose ^a	Day 2, Week 1 ^g	Day 15, Week 3 +/- 3 days	Day 29, Week 5 +/- 3 days	Day 57, Week 9 +/- 7 days	Day 85, Week 13 +/- 7 days	Day 113, Week 17 +/- 7 days	Day 141, Week 21 +/- 7 days	Day 169, Week 25 +/- 7 days	Day 197, Week 29 +/- 7 days	Unscheduled Visit
Informed Consent ^k	X												
Inclusion/Exclusion Criteria	X	X											
Height	X												
Weight	X	X			X	X	X	X	X	X	X	X	X
Physical exam/med. History PDAI/ABSIS	X												
Abbreviated physical exam, PDAI, ABSIS		X			X	X	X	X	X	X	X	X	X
ECG (12-lead)	X												(X) ^b
Vital Signs ^j	X	X		X	X	X	X	X	X	X	X	X	X
Urinalysis	X												
Hep B & C, HIV, T- spot TB Test, QuantiFERON®-TB Gold, QuantiFERON®-TB Gold Plus (QFT Plus)	X												
Pregnancy test ^c	X	X				X	X	X	X	X	X	X	
Skin biopsy ^d	X												
Hem, Coag, Chem	X ^e	X			X	X	X	X	X	X	X	X	X
FSH ^f	X												
BTK occupancy sample		X ^g	X ^h	X	X	X	X	X	X	X	X		(X) ^b
PK sample		X	X ^h	X ^a	X	X	X	X	X	X	X		(X) ^b
Anti-DSG antibodies		X				X	X	X	X	X	X	X	

	Screen	Day 1, Week 1 Pre-dose	Day 1 Week 1 Post-dose ^a	Day 2, Week 1 ^b	Day 15, Week 3 +/- 3 days	Day 29, Week 5 +/- 3 days	Day 57, Week 9 +/- 7 days	Day 85, Week 13 +/- 7 days	Day 113, Week 17 +/- 7 days	Day 141, Week 21 +/- 7 days	Day 169, Week 25 +/- 7 days	Day 197, Week 29 +/- 7 days	Unscheduled Visit
Photography (Optional) ⁱ		X			X	X	X	X	X	X	X	X	X
ABQOL & TABQOL		X			X	X	X	X	X	X	X	X	X
SNAQ questionnaire		X				X	X	X	X	X	X	X	X
AEs		X		X	X	X	X	X	X	X	X	X	X
Concomitant Medications	X	X		X	X	X	X	X	X	X	X	X	X
Drug dispensed		X				X	X	X	X	X			
Drug reconciliation					X	X	X	X	X	X	X	X	

- a. Withhold PRN1008 on morning of Day 2 until PK/PD measurement has been taken as close to 12 hours (when *bid* dosing) or 24 hours (when *qd* dosing) after the prior dose as possible. Where follow-up on Day 2 is not possible, PK/PD samples may be taken on another day in the first week of treatment. On all other days, instruct patient to take PRN1008 in the morning as usual prior to clinic and take note of the time taken. Extra PK/PD sample intended for 1 to 5 days after dose adjustment or to replace missing samples—not required for other extra visits.
- b. Only if clinically indicated.
- c. For women of childbearing potential only. Serum pregnancy test done at screening, urine dip test done at other time points.

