5.4.1 Primary Efficacy Endpoint

The primary efficacy endpoint is:

- The proportion of patients who are able to achieve CDA within 4 weeks (on or prior to Week 5 visit) of starting PRN1008 treatment **without** the need for doses of prednis(ol)one > 0.5 mg/kg

The Control of Disease Activity (CDA) responses are assessed at visits specified in the Schedule of assessments (Table 1). Types of CS other than prednis(ol)one are converted to dose-equivalent prednis(ol)one (see Section 5.4.2.3).

This is operationalized as meaning the first CDA is achieved on or before the Week 5 visit but after first dose of PRN1008, and will be summarized, by dose level to the Week 5 visit and overall in a table, using frequencies and percentages. In addition, two-sided 80% and 95% CIs (Confidence Intervals) of the response rate will be provided for each dose level and overall.

Patients who are able to achieve CDA between first dose of study drug and the Week 5 visit without prednis(ol)one >0.5 mg/kg on the date prior to the CDA will be considered as responders, even if the CDA status was not maintained or higher doses of prednis(ol)one were used after the first CDA. Patients who are not able to achieve CDA prior to or at the Week 5 visit or had prednis(ol)one >0.5 mg/kg on the date prior to CDA will be considered as non-responders. Patients whose CDA status is unknown at the Week 5 visit for whatever reason (including early termination before Week 5 visit) will be also considered as non-responders. Only systemic CSs (as defined by medication taken orally or intravenously) are to be used to evaluate the efficacy endpoints, topical CSs (including buccal CS) will not be counted.

The number and percentage of patients who meet the primary efficacy endpoint criteria will be tabulated by dose level and overall (all patients).

A sensitivity analysis using the Completer and PP population will be provided.

Panel plots will be provided for PDAI score over the study period for each patient. Dose level (mg/day) will also be plotted on the same figure. Lines for the steroid equivalent dose in mg/kg will be added to the plots. A total of 9 plots (3 x 3) will be fitted on one page.

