>=80 % and < 100 %	x (x.x)	x (x.x)	x (x.x)	x (x.x)
< 80%	x (x.x)	x (x.x)	x (x.x)	x (x.x)

The duration of exposure at each dose level is the date of last dose in a given dose level – date of first dose in the same dose level + 1.

The duration of exposure for “Overall” is date of last dose – date of first dose + 1.

Calculated dose in mg/day at each dose level = [Dose level (mg/day) x (Duration of exposure (x2 if BID) – doses missed)]/Duration of Exposure.

Compliance with study drug = the actual number of doses taken divided by the expected number of doses take, expressed as a percentage.

Program: <program name (date, time)>, Path: <path>

Table B.14.2.1.1.1 Proportion of patients Achieved CDA at or Prior to Week 5 without prednis(ol)one >0.5 mg/kg (mITT Population)

Achieved CDA at or Prior to Week 5 without prednis(ol)one >0.5 mg/kg	400 mg QD (N = n)	400 mg BID (N = n)	600 mg BID (N = n)	Overall (N = n)
N achieved (%)	x (x.x)	x (x.x)	x (x.x)	x (x.x)
- 80% CI	x.xx, x.xx	x.xx, x.xx	x.xx, x.xx	x.xx, x.xx
- 95% CI	x.xx, x.xx	x.xx, x.xx	x.xx, x.xx	x.xx, x.xx

Percentages are based on the number of patients in each dose group and overall.

Patients are classified into different dose levels according to the dose they received prior to achieving CDA.

Confidence Intervals are based on the Exact (Clopper-Pearson) method.

Primary efficacy endpoint: Proportion of patients who achieved CDA within 4 weeks of starting PRN1008 treatment, i.e. At or prior to Week 5, without prednis(ol)one equivalent > 0.5 mg/kg on the day prior to the assessment.

Program: <program name (date, time)>, Path: <path>

Table B.14.2.1.1.2 Proportion of patients Achieved CDA at or Prior to Week 5 without prednis(ol)one >0.5 mg/kg (Completer Population)

Table B.14.2.1.1.3 Proportion of patients Achieved CDA at or Prior to Week 5 without prednis(ol)one >0.5 mg/kg (PP Population)

Table B.14.2.1.2.1 Proportion of patients Achieved CDA at or Prior to Week 5 without prednis(ol)one >0.5 mg/kg – Subgroup – Age (mITT Population)

Subgroup	Achieved CDA at or Prior to Week 5 without prednis(ol)one >0.5 mg/kg	400 mg QD (N = n)	400 mg BID (N = n)	600 mg BID (N = n)	Overall (N = n)
Age < 50	Number of patients	n	n	n	n
	N achieved (%)	x (x.x)	x (x.x)	x (x.x)	x (x.x)
	- 80% CI	x.xx, x.xx	x.xx, x.xx	x.xx, x.xx	x.xx, x.xx
	- 95% CI	x.xx, x.xx	x.xx, x.xx	x.xx, x.xx	x.xx, x.xx
Age ≥ 50	Number of patients	n	n	n	n
	N achieved (%)	x (x.x)	x (x.x)	x (x.x)	x (x.x)

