n	x.xx (x.xxx)	x.xx (x.xxx)	x.xx (x.xxx)	x.xx (x.xxx)
Mean (SD)	x.xx	x.xx	x.xx	x.xx
Median	x.x, x.x	x.x, x.x	x.x, x.x	x.x, x.x
Min, Max				

Duration of CR = Last Known CR Date – First Known CR Date + 1.

Patients are classified into different dose levels according to the dose they received prior to achieving CR.

Table B.14.2.2.16.2 Duration of Complete Remission (CR) (Completer Population)

Table B.14.2.2.16.3 Duration of Complete Remission (CR) (PP Population)

Table B.14.2.2.17.1 Time to First CDA: Kaplan Meier Estimates (mITT Population)

	400 mg QD (N = n)	400 mg BID (N = n)	600 mg BID (N = n)	Overall (N = n)
Time to first CDA (days) [1]				
n	x	x	x	x
25% Quartile	x.x	x.x	x.x	x.x
- 80% CI	(x.xx, x.xx)	(x.xx, x.xx)	(x.xx, x.xx)	(x.xx, x.xx)
- 95% CI	(x.xx, x.xx)	(x.xx, x.xx)	(x.xx, x.xx)	(x.xx, x.xx)
Median	x.x	x.x	x.x	x.x
- 80% CI	(x.xx, x.xx)	(x.xx, x.xx)	(x.xx, x.xx)	(x.xx, x.xx)
- 95% CI	(x.xx, x.xx)	(x.xx, x.xx)	(x.xx, x.xx)	(x.xx, x.xx)
75% Quartile	x.x	x.x	x.x	x.x
- 80% CI	(x.xx, x.xx)	(x.xx, x.xx)	(x.xx, x.xx)	(x.xx, x.xx)
- 95% CI	(x.xx, x.xx)	(x.xx, x.xx)	(x.xx, x.xx)	(x.xx, x.xx)
Min, Max [2]	x , x	x , x	x , x*	x , x*
Kaplan-Meier estimates % (n) [3]				
15 Days	x.x (xx)	x.x (xx)	x.x (xx)	x.x (xx)
29 Days	x.x (xx)	x.x (xx)	x.x (xx)	x.x (xx)
57 Days	x.x (xx)	x.x (xx)	x.x (xx)	x.x (xx)
85 Days	x.x (xx)	x.x (xx)	x.x (xx)	x.x (xx)
113 Days	x.x (xx)	x.x (xx)	x.x (xx)	x.x (xx)
141 Days	x.x (xx)	x.x (xx)	x.x (xx)	x.x (xx)
169 Days	x.x (xx)	x.x (xx)	x.x (xx)	x.x (xx)

Patients are classified into different dose levels according to the dose they received at a given visit.

[1] Time to first CDA in days will be calculated as: Date of first occurrence of CDA – Date of first study drug dosing of the dose level where the CDA is observed + 1.

Patients who did not achieve CDA are censored at the last day in a dose level or date of study completion/discontinuation. 80% and 95% confidence intervals are calculated using the LOGLOG transformation.

[2] * indicates that this value is from a censored data.

[3] Kaplan-Meier estimate of the probability of experiencing the event on or before the specified timepoint (n = number of patients remaining at risk beyond the specified timepoint.)

Program: <program name (date, time)>, Path: <path>

Table B.14.2.2.17.2 Time to First CDA: Kaplan Meier Estimates (Completer Population)

Table B.14.2.2.17.3 Time to First CDA: Kaplan Meier Estimates (PP Population)

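### As written, the Part B time-to-event clock restarts at each dose level even in the Overall column, so times after escalation are short by nominally at least 14 or 28 days; the dose columns also censor at response-driven escalation

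*SAP*

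**What the plan says.** Part B SAP Section 5.4.2.2 covers first CDA, CR, ECP, relapse and PDAI increase, analysed for each dose level and overall. One formula serves them all: event date, minus the "Date of first study drug dosing of the dose level where the event is observed", plus one. The footnote of Table B.14.2.2.17.1 repeats it for CDA ("Date of first study drug dosing of the dose level where the CDA is observed"). That shell has an Overall column and landmarks from 15 to 169 days. On censoring, Section 5.4.2.2 says: "Patients who did not achieve the specific event are censored at the last day in a dose level or date of study completion/discontinuation". It does not say which date belongs to which column.

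Related text elsewhere:

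- **Exposure, Table B.14.1.8.2.** Overall has its own rule: its duration "is date of last dose – date of first dose + 1".
- **Part A, Table 14.2.3.1.1.** "Time to first CDA = Date of first CDA confirmed - Date of first dose + 1". Part A SAP Section 8.2.6 agrees.
- **Primary endpoint, Part B SAP Section 5.4.1.** "Patients who are not able to achieve CDA prior to or at the Week 5 visit" are non-responders.
- **Escalation, Part B SAP Section 2.2.** Dosing starts at 400 mg qd, "with intra-patient dose escalation to 400 mg bid allowed at or after the Week 3 visit for insufficient clinical response", with a further step to 600 mg bid from Week 5. The schedule in Section 2.7 sets "Day 15, Week 3 +/- 3 days" and the same window around Day 29.
- **Dose columns, Part B SAP Section 5.4.** A dose column includes every patient who ever took that dose.
- **Relapse.** Protocol Section 11.2 times relapse from stopping PRN1008. Part B SAP Section 5.4.2.2 takes relapse after the first dose. Section 4.7 does not list this change and describes its rewording of endpoints as leaving their meaning intact.

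**The concern.** Time since starting 400 or 600 mg bid can be defined as an on-dose quantity. It is not time to first response from the start of treatment, which is what an Overall column would be read as. The protocol synopsis wants the study to approximate the response rate and the average time to response for planning pivotal trials, and allows the two Parts to be combined where appropriate. A restarted clock would make Part B look faster than it was and put its times on a different footing from Part A's.

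The dose columns raise a second problem. Patients leave 400 mg qd because they are not responding well enough. Treating them as ordinary censored observations lets those who stay stand in for them.

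**Working it through.** **The plan's own figure.** The only design figure, in Part B SAP Section 2.3, is an 80% interval of ±13% at a 50% response rate with 25 patients: 1.2816 × √(0.5 × 0.5/25) = 0.128. It reproduces, but does not bear on this point. No median or event count is stated for the time-to-event endpoints.

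**Step 1: days lost in Overall.** Take the new dose as starting on the visit day.

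Days lost = (event day − 1 + 1) − (event day − level start day + 1) = level start day − 1.

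| New level starts | Days lost | With the ±3-day window |
|---|---|---|
| Day 15 | 14 | 11 to 17 |
| Day 29 | 28 | 25 to 31 |
| Day 57 | 56 | – |

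Escalation may come at or after Weeks 3 and 5, so 14 and 28 are nominal minimums.

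**Step 2: landmarks.** Escalated Day 29, CDA dated Day 57: 57 − 29 + 1 = 29, an event by 29 days. Section 5.4.1 calls this patient a Week 5 non-responder, and the cumulative incidence by visit (Section 5.4.2.1) would not count the response until Week 9. Escalated Day 15, CDA on Day 29: 29 − 15 + 1 = 15. In a table of 25 without earlier censoring, each such patient adds 1/25 = 4 points to the landmark.

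Constructed example: 8 patients reach CDA on qd on Day 29, 9 escalate on Day 29 and reach CDA on Day 57, and 8 never do. Overall by 29 days is 8/25 = 32% from first dose, and 17/25 = 68% as written.

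**Step 3: mean time among responders.** The documents give no escalation or response rates. Assume 5 patients with CDA on qd on Day 15, 3 on Day 29, and m escalated on Day 15 with CDA on Day 29.

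- From first dose: (5×15 + 3×29 + 29m)/(8 + m)
- As written: (5×15 + 3×29 + 15m)/(8 + m)

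| m | From first dose | As written | Short by |
|---|---|---|---|
| 2 | 22.0 | 19.2 | 2.8 |
| 5 | 23.6 | 18.2 | 5.4 |
| 8 | 24.6 | 17.6 | 7.0 |

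**Step 4: patients without the event.** They have no level where the event is observed, so the formula gives no start date. The choice between two censoring dates is also open. The Overall curve cannot be programmed unambiguously.

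**Step 5: the 400 mg qd column.** Times here are not shortened. Assume 25 patients, 5 events on Day 15, k escalated and censored on Day 15, and 3 events on Day 29.

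Kaplan-Meier by Day 29 = 1 − (20/25)(1 − 3/(20 − k)).

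Let f be the chance that an escalated patient would have responded on qd by Day 29, relative to those kept on it. The value had nobody escalated is (8 + f × k × 3/(20 − k))/25.

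| k | Kaplan-Meier | Excess, f = 0 | Excess, f = 0.5 | Excess, f = 1 |
|---|---|---|---|---|
| 4 | 35% | 3 points | 1.5 | 0 |
| 8 | 40% | 8 points | 4 | 0 |
| 12 | 50% | 18 points | 9 | 0 |

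Holding the Day 29 events at 3 means that the response rate of those who stay rises with k, from 3/16 = 19% to 3/8 = 38%. The table shows direction and range; it is not a forecast.

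**The case against.** The best defence is that the Overall rule is implied. Sections 5.3 and 5.3.1 promise exposure by dose level and overall but give only a dose-level formula; the Overall rule appears in the shell footnote. The censoring sentence fits the same habit, with the end of a dose level suiting the dose columns and study end suiting Overall. A programmer might well use the first dose. Sections 3.2.8 (patients from Part A) and 3.3 (treatment groups) are named in the contents but were not available for review, and may define the columns. This limits certainty about what was intended. It does not remove the explicit formula, which the time-to-event footnote repeats without the Overall exception that the exposure footnote has.

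The harm is bounded, too. Protocol Section 11.2 names no origin for time to CDA or CR, so it is not contradicted there. Neither SAP specifies a pooled time-to-event analysis. The overall cumulative incidence by visit shows the CDA and CR time course correctly, and event dates are listed by patient.

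Three stronger readings might be inferred and are not supported:

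- **That the primary result is affected.** It counts from the start of PRN1008, and the overall proportion does not use this formula.
- **That the qd estimates are certainly too high.** At f = 1 there is no excess. The argument also does not extend to relapse or PDAI increase.
- **That cumulative incidence with escalation as a competing event is the correct replacement.** In Step 5 it gives 8/25 = 32% throughout, which at f = 1 is 3, 8 or 18 points below the value had nobody escalated. It answers a different question.

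**Conclusion.** The concern holds as a fault in the rule as written. Taken literally, Overall times after escalation are short by the level start day minus one: nominally at least 14 days for Week 3 escalation or 28 for Week 5. The Overall landmarks then conflict with the Week 5 responder rule and the cumulative incidence by visit, and use a different origin from Part A. The days lost follow from the formula; the effect on means and percentages rests on assumed rates.

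The qd column's Kaplan-Meier estimates for CDA, CR and ECP can read too high, as can the 400 mg bid column's for patients moved to 600 mg bid. The size is unknown. The undeclared change to relapse is a separate fault in the same section.

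All of this concerns descriptive secondary results, with no hypothesis testing planned (Section 3.8). It is worth correcting because average time to response is one of the study's stated uses.

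**What to change.** 1. In Section 5.4.2.2 and the Table B.14.2.2.17.1 footnote, carried to the CR, ECP and PDAI-increase tables, state for Overall: *Time to event = date of first event − date of first PRN1008 dose in Part B + 1; patients without the event are censored when they complete or leave the study, not at dose change.* Check this against Sections 3.2.8 and 3.3.
2. Label the dose-level columns as time since starting that dose. Add a footnote that censoring at escalation is response-related, so these Kaplan-Meier estimates should not be read as response probabilities on that dose. Competing-event cumulative incidence may be added, but is optional.
3. For relapse, restrict the analysis to patients who achieved CDA; otherwise those who never reach it count as at risk. Either restore the protocol's time to relapse after stopping PRN1008, or list its replacement in Section 4.7.

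The cost is SAP and footnote wording and reprogramming of Tables B.14.2.2.17 to B.14.2.2.21. No new data are needed: event dates and dose-level dates are already in Listings B.16.2.6.1 and B.16.2.5.2.
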